Incidence of ECMO by day 14 [study day based on Date]	
Transition to ECMO (Y/N) is collected in "Ventilation - Specific Information" CRF Daily assessments through extubation.
 
Incidence of ECMO at Day 14 :
 
event = "Y" if Transition to ECMO = "Y" and date of daily collection (VSIDAT) is performed between date of 1st IMP intake and Day 14 included.
 
otherwise
 
event = "N" if last available day ≥ 12 (allowed time window of 2 day for Day 14 visit)
 
otherwise event is missing if last available day < 12
 
Day 14= Day1 (date 1st IMP intake) + 13

Standard/Forms/Template				
Title		Statistical Analysis Plan Template		
Code		Version	Effective Date	Page
PPD		01	29 Aug 2022	67 of 78

Parameter	Calculation
Use of Vasoactive Medication by day 14 [study day based on Date/time]	
Use of Vasoactive Medications is collected in "Ventilation - Specific Information" CRF Daily assessments through extubation.
 
Use of Vasoactive Medications by Day 14 :
 
event = "Y" if Vasoactive Medications = "Y" and date/time of daily collection is performed between Date/time of 1st IMP intake and Day 14 (date/time).
 
otherwise
 
event = "N" if last available day>=12 (allowed time window of 2 day for Day 14 visit)
 
otherwise event is missing if last available day<12
 
Day 14= Day1 (date/time 1st IMP intake) + 13

Incidence of tracheostomies by day 28 and hospital discharge [study visit]	
Performance of tracheostomy (Y/N) and date of tracheostomy is collected in "Other Clinical Event" CRF Form.
 
Incidence of tracheostomy by Day 28 :
 
event = "Y" if date of tracheostomy is performed between date of 1st IMP intake and Day 28 visit date.
 
otherwise event = "N" if ((date of tracheostomy is missing or < date 1st IMP intake) and day 28 visit is present) or (date of tracheostomy > day 28 visit)
 
otherwise event is missing if day 28 visit is missing.
 
Incidence of tracheostomy by hospital discharge:
 
event = "Y" if date of tracheostomy is performed between date of 1st IMP intake and date of Hospital Discharge* (included). In the case the discharge date is missing (but the date of tracheostomy is not missing), it is assumed that the patient is at the hospital (as the tracheostomy can only be performed at the hospital) therefore the event will be = "Y".
 
otherwise event = "N" if ((date of tracheostomy is missing or < date 1st IMP intake) and date hospital discharge* is present) or (date of tracheostomy > hospital discharge*)
 
otherwise event is missing .
 
note: if date hospital discharge is missing and patient died then date hospital discharge* = date death.
 
*date of discharge is collected in EOS; in the case it is missing it is taken from Visit date in "Hospital Discharge".

Standard/Forms/Template				
Title		Statistical Analysis Plan Template		
Code		Version	Effective Date	Page
PPD		01	29 Aug 2022	68 of 78

Parameter	Calculation
Incidence of LTAC facility by day 28 and hospital discharge [study visit]	
Performance of LTAC facility (Y/N) and date of LTAC facility is collected in "Other Clinical Event" CRF Form.
 
Incidence of LTAC facility by Day 28 :
 
event = "Y" if date of LTAC facility is performed between date of 1st IMP intake and Day 28 visit date.
 
otherwise event = "N" if ((date of LTAC facility is missing or < date 1st IMP intake) and day 28 visit is present) or (date of LTAC facility > day 28 visit)
 
otherwise event is missing if day 28 visit is missing
 
Incidence of LTAC facility by hospital discharge:
 
event = "Y" if date of LTAC facility is performed between date of 1st IMP intake and Date of Hospital Discharge* (included). In the case the discharge date is missing (but the date of LTAC facility is not missing), it is assumed that the patient is at the hospital therefore the event will be = "Y".
 
otherwise event = "N" if ((date of LTAC facility is missing or < date 1st IMP intake) and date hospital discharge* is present) or (date of LTAC facility > hospital discharge*)
 
otherwise event is missing if hospital discharge is missing
 
note: if date hospital discharge* is missing and patient died then date hospital discharge* = date death
 
*date of discharge is collected in EOS; in the case it is missing it is taken from Visit date in "Hospital Discharge".

Standard/Forms/Template				
Title		Statistical Analysis Plan Template		
Code		Version	Effective Date	Page
PPD		01	29 Aug 2022	69 of 78

Ventilatory Ratio (VR) [study day based on date/time]	
As per Protocol Section 14.4.4. (From: Sinha P et al. Physiologic analysis and clinical performance of the ventilatory ratio in acute respiratory distress syndrome. Am J Respir Crit Care Med 2019; 199: 333-341)
 
VR = [minute ventilation (ml/min) × PaCO₂ (mm Hg)]/[predicted body weight × 100 (ml/min) × 37.5 (mm Hg)]
 
Where:
 
Predicted body weight (PBW):
 
Males = 50 + 2.3 [height (inches) – 60], where height(inches) = height(cm)/2.54
 
Females = 45.5 + 2.3 [height (inches) – 60], where height(inches) = height(cm)/2.54
 
minute ventilation (ml/min)= the product of the tidal volume and breathing frequency.
 
- Tidal volume (ml) is collected under "Mechanical Ventilation Parameters" at "randomization and baseline assessments "and during the daily assessment through extubation. Mechanical Ventilation Parameters are collected at a specific date and time.
 
- Breathing frequency is collected under "Respiration Rate (n/min)" in "Vital Signs" collected at "randomization and baseline assessments", during the daily assessments through extubation, during "assessments from extubation to hospital discharge (every 48h+/-8h)". Vital Signs are collected at a specific date and time.
 
-PaCO₂ (mm Hg)= collected under "Lung Function" at "Screening day -1 or 1", "randomization and baseline assessments" during the "daily assessment through extubation", during "assessments from extubation to hospital discharge (every 48h+/-8h)", at day 28 and at hospital discharge
 
Ventilatory Ratio (VR) at baseline:
 
1 - For each day on or prior treatment start date/time, derive VR as defined below.
 
"Ventilatory Rate" derivation for each pre-treatment start day:
 
1.1 - Select the last record of "Tidal Volume" collected in that day (if on the same date of treatment start date, use only records with time <= time of first exposure to IMP)
 
1.2 - Select the "Respiratory Rate" closest to the selected "Tidal Volume" and occurring on the same timeframe (tidal volume date/time +/- 12h) but assessed on or prior treatment start date/time. If no value exists in the timeframe of +/- 12h, use the value of "Respiratory Rate" that is closest to the selected "Tidal Volume" date/time but collected in the exact same date (only consider values collected prior treatment start date/time). If there is no match, set the at baseline as missing.
 
Note: In case of multiple records at same distance, use the value collected under "Randomization" visit, if available. Otherwise, use the one collected under the latest timepoint

---	---

Standard/Forms/Template				
Title		Statistical Analysis Plan Template		
Code		Version	Effective Date	Page
PPD		01	29 Aug 2022	70 of 78

Parameter	Calculation
	
prior treatment start date (i.e.: by order: 1 - "Screening", 2 - "Daily assessments through extubation").
 
1.3 - Select the "PaCO2" closest to the selected "Tidal Volume" and occurring on the same timeframe (tidal volume date/time +/- 12h) but assessed on or prior treatment start date/time. If no value exists in the timeframe of +/- 12h, use the value of "PaCO2" that is closest to the selected "Tidal Volume" date/time but collected in the exact same date (only consider values collected prior treatment start date/time). If there is no match, set the baseline as missing
 
Note: In case of multiple records at same distance, use the value collected under "Randomization" visit, if available. Otherwise, use the one collected under the latest timepoint prior treatment start date (i.e.: by order: 1 - "Screening", 2 - "Daily assessments through extubation").
 
1.4 - Derive the "VR" using the values selected above.
 
2 - Select the VR record closest to the treatment start date.
 
Note: It's expected that the VR will be derived from the assessments performed on the same day of treatment start date (day 1). If VR not available on day 1, then use the VR available from exact previous day (TRTSDT-1). In case neither exists, then the baseline will be missing.
 
Ventilatory Ratio (VR) at day 2: day 2 will be derived as per section 3.2 based on date and time (i.e., for day 2 from 12h after 1st IMP intake to 35h and 59 minutes after 1st IMP intake): if in the pre-specified window for day 2, there are measurements of tidal volume and respiration rate and PaCO2 (they do not need to be collected the same date/time), then VR is computable. Otherwise, it will be set as missing. If more than one assessment is available within the window of day 2, keep the assessment closer to the midpoint of the time interval. For instance: 2 assessments at day 2, the one closer to 24hours from 1st IMP will be taken. If multiple records exist at the same distance from the midpoint of the time interval, select the first record collected in the eCRF. Derive the VR using the selected values.
 
In case PaCO2 and/or minute ventilation is missing at a day, the value of VR for that day is not derived.
 
Ventilatory Ratio at day 3, 7, 14 : same as for day 2.


Standard/Forms/Template			
Title	Statistical Analysis Plan Template		
Code	Version	Effective Date	Page
PPD	01	29 Aug 2022	71 of 78

Acute lung injury score [by visit and date/time]	
As per study protocol, acute lung injury score is a composite value of $\text{PaO}_2/\text{FiO}_2$ ratio, PEEP, lung compliance (plateau airway pressure minus PEEP/TV) and extent of pulmonary infiltrates.
 
  
 		Value	
   
 1. Chest X-ray (Number of quadrants with alveolar infiltrates)			
 
 0		0	
 
 1 quadrant		1	
 
 2 quadrants		2	
 
 3 quadrants		3	
 
 4 quadrants		4	
 
 2. Hypoxemia score ($\text{PaO}_2/\text{FiO}_2$ mmHg)			
 
 $\text{PaO}_2/\text{FiO}_2$	$\geq 300$	0	
 
 $\text{PaO}_2/\text{FiO}_2$	225-<300	1	
 
 $\text{PaO}_2/\text{FiO}_2$	175-<225	2	
 
 $\text{PaO}_2/\text{FiO}_2$	100-<175	3	
 
 $\text{PaO}_2/\text{FiO}_2$	<100	4	
 
 3. PEEP score (cmH₂O)			
 
 PEEP	≤ 5 cmH₂O	0	
 
 PEEP	6-8.99 cmH₂O	1	
 
 PEEP	9-11.99 cmH₂O	2	
 
 PEEP	12-14.99 cmH₂O	3	
 
 PEEP	≥ 15 cmH₂O	4	
 
 4. Compliance (ml/cmH₂O)			
 
 Compliance	≥ 80 ml/cmH₂O	0	
 
 Compliance	60-79.99 ml/cmH₂O	1	
 
 Compliance	40-59.99 ml/cmH₂O	2	
 
 Compliance	30-39.99 ml/cmH₂O	3	
 
 Compliance	≤ 29.99 ml/cmH₂O	4	
  
 
* Abbreviations: $\text{Pao}_2/\text{Flo}_2$ = arterial oxygen tension to inspired oxygen concentration ratio; PEEP =: positive end-expiratory pressure.
 
The value of acute injury score is obtained by a mean of the items reported in the table above i.e., by dividing the aggregate sum by the number of components that were used (Protocol Section 14.4.5).
 
The acute injury score is computable only if 3 over 4 items (of the table above) are not missing.
 
The score will be classified as follows:
 
  
 	Score	
   
 No lung injury	0	
 
 Mild-to-moderate lung injury	0.1-2.5	
 
 Severe lung injury (ARDS)	>2.5	
  
 
Alveolar infiltrates are collected under "Chest Imaging" collected at "Screening day -1 or 1", "randomization and baseline assessments", at day 2, day 3, day 7, day 14
			Value	1. Chest X-ray (Number of quadrants with alveolar infiltrates)			0		0	1 quadrant		1	2 quadrants		2	3 quadrants		3	4 quadrants		4	2. Hypoxemia score ($\text{PaO}_2/\text{FiO}_2$ mmHg)			$\text{PaO}_2/\text{FiO}_2$	≥ 300	0	$\text{PaO}_2/\text{FiO}_2$	225-<300	1	$\text{PaO}_2/\text{FiO}_2$	175-<225	2	$\text{PaO}_2/\text{FiO}_2$	100-<175	3	$\text{PaO}_2/\text{FiO}_2$	<100	4	3. PEEP score (cmH ₂ O)			PEEP	≤ 5 cmH ₂ O	0	PEEP	6-8.99 cmH ₂ O	1	PEEP	9-11.99 cmH ₂ O	2	PEEP	12-14.99 cmH ₂ O	3	PEEP	≥ 15 cmH ₂ O	4	4. Compliance (ml/cmH ₂ O)			Compliance	≥ 80 ml/cmH ₂ O	0	Compliance	60-79.99 ml/cmH ₂ O	1	Compliance	40-59.99 ml/cmH ₂ O	2	Compliance	30-39.99 ml/cmH ₂ O	3	Compliance	≤ 29.99 ml/cmH ₂ O	4		Score	No lung injury	0	Mild-to-moderate lung injury	0.1-2.5	Severe lung injury (ARDS)	>2.5
		Value																																																																																		
1. Chest X-ray (Number of quadrants with alveolar infiltrates)																																																																																				
0		0																																																																																		
1 quadrant		1																																																																																		
2 quadrants		2																																																																																		
3 quadrants		3																																																																																		
4 quadrants		4																																																																																		
2. Hypoxemia score ($\text{PaO}_2/\text{FiO}_2$ mmHg)																																																																																				
$\text{PaO}_2/\text{FiO}_2$	≥ 300	0																																																																																		
$\text{PaO}_2/\text{FiO}_2$	225-<300	1																																																																																		
$\text{PaO}_2/\text{FiO}_2$	175-<225	2																																																																																		
$\text{PaO}_2/\text{FiO}_2$	100-<175	3																																																																																		
$\text{PaO}_2/\text{FiO}_2$	<100	4																																																																																		
3. PEEP score (cmH ₂ O)																																																																																				
PEEP	≤ 5 cmH ₂ O	0																																																																																		
PEEP	6-8.99 cmH ₂ O	1																																																																																		
PEEP	9-11.99 cmH ₂ O	2																																																																																		
PEEP	12-14.99 cmH ₂ O	3																																																																																		
PEEP	≥ 15 cmH ₂ O	4																																																																																		
4. Compliance (ml/cmH ₂ O)																																																																																				
Compliance	≥ 80 ml/cmH ₂ O	0																																																																																		
Compliance	60-79.99 ml/cmH ₂ O	1																																																																																		
Compliance	40-59.99 ml/cmH ₂ O	2																																																																																		
Compliance	30-39.99 ml/cmH ₂ O	3																																																																																		
Compliance	≤ 29.99 ml/cmH ₂ O	4																																																																																		
	Score																																																																																			
No lung injury	0																																																																																			
Mild-to-moderate lung injury	0.1-2.5																																																																																			
Severe lung injury (ARDS)	>2.5																																																																																			

Standard/Forms/Template				
Title		Statistical Analysis Plan Template		
Code		Version	Effective Date	Page
PPD		01	29 Aug 2022	72 of 78

Parameter	Calculation
	
PaO₂/FiO₂ (mmHg) is collected under "Lung Function" at "Screening day -1 or 1", "randomization and baseline assessments", during the "daily assessment through extubation", during "assessments from extubation to hospital discharge (every 48h+/-8h)", at day 28 and at hospital discharge.
 
PEEP (cmH₂O) and Compliance (ml/cmH₂O) is collected under "Mechanical Ventilation Parameters" at "randomization and baseline assessments" and during the daily assessment through extubation. Mechanical Ventilation Parameters are collected at a specific date and time
 
Rules to match assessments for Acute Lung Injury score:
 
 1. keep date of Chest Imaging assessment from the i-th visit (namely, day 2,3,7,14) 2. link date of LF (Lung Function) and MV (Mechanical Ventilation) assessments with the date of CI (Chest Imaging), i.e., the assessments should be at the same date. 3. If no link is feasible Acute Lung Injury Score at that Visit will be missing. 
If chest imaging date is missing, please use study day based on date/time as follows:
 
Select the value of Lung Function assessment based on the study day rules considering date and time. Select the value Mechanical Ventilation assessment based on the study day rules considering date and time. If there is one measurement of LF and one measurement of MV falling in that specific study day (as defined by the rules considering date/time), select these values to compute the Acute Lung Injury score at that day. Do the same for each applicable post baseline day. (Example for day 7. Both LF and MV assessments should be collected in the window [First IMP Intake+132h, First IMP Intake+155h and 59min]). In case of more assessments at the same day, keep the assessment closer to the midpoint of the time interval. For instance: 2 assessments at day 7 [First IMP Intake Date/Time +132h, First IMP Intake Date/Time +155h and 59 min], the one closer to 144 hours from 1st IMP will be taken. If multiple records exist at the same distance from the midpoint of the time interval, select the first record collected in the eCRF.

SOFA score [study day based on date/time]	
The SOFA score is calculated as per Study Protocol section 14.4.2, and it is collected in CRF at "randomization and baseline assessments" and during the daily assessment through extubation.
 
SOFA score is calculated every 24 hours using (for each organ system) the worst variable recorded within the same 24 hours. The best possible score corresponds to 0 whereas the worst score corresponds to 24.
 
The SOFA total score will be considered as collected in CRF.
 
Study day will be presented using date/time (as described in section 3.2). In the case more than one assessment is eligible for the time windows described in section 3.2 for a specific day, the assessment closest to the midpoint of that day will be considered.

Standard/Forms/Template				
Title		Statistical Analysis Plan Template		
Code		Version	Effective Date	Page
PPD		01	29 Aug 2022	73 of 78

Parameter	Calculation
RALE score [by visit]	
The RALE score is calculated as per Study Protocol section 14.4.3, and it is collected in CRF under "Chest Imaging" at "Screening day -1 or 1", "randomization and baseline assessments", at day 2, day 3, day 7, day 14.
 
The RALE score will be considered as collected in CRF.
 
Study day will be presented by visit.

Secondary infections	
Secondary infections are flagged in the AE CRF Form via the field "Is the AE a secondary infection? " (Y/N)
 
Secondary infections by Day 28: are defined as those secondary infections collected up to day 30 (upper limit of Day 28 visit)
 
Secondary infections by Hospital Discharge: are defined as those secondary infections collected up to the subject's date for Hospital discharge*. If the subject has no hospital discharge it is assumed is because the subject was not discharged, so it is assumed that the infection was during the hospitalization; if the subject has no hospital discharge and also no secondary infection, the subject will not be considered in the analysis.
 
*date of discharge is collected in EOS; in the case it is missing it is taken from Visit date in "Hospital Discharge".

All-cause mortality by day 28 and by day 60 [study day based on Date]	
The following algorithm is implemented.
 
Death at day 28:
 
If patient died up to Day 28* (included) then endpoint = "Y"
 
Else if Last available day\geq26* then endpoint = "N"
 
Else If Last available day$<$26* endpoint is missing.
 
Death at day 60*: use the time window (+/-2)
 
If patient died up to Day 60* (included) is endpoint = "Y"
 
Else if Last available day\geq58* then endpoint = "N"
 
Else If Last available day$<$58* endpoint is missing.
 
*Day 28= Day1 (date 1st IMP intake) + 27; similar derivation for day 26, 60, 58 mentioned above

Standard/Forms/Template				
Title		Statistical Analysis Plan Template		
Code		Version	Effective Date	Page
PPD		01	29 Aug 2022	74 of 78

Parameter	Calculation
Percentage of patients achieving pressure support ventilation equal to 5 cmH ₂ O with PEEP equal to 5 cmH ₂ O for 2 hours (measure of weaning) by day 28 and at hospital discharge [study day: date]	
As per study protocol, CPAP (Continuous Positive Airway Pressure) is defined as use of pressure support ventilation equal to 5 cmH₂O with PEEP equal to 5 cmH₂O for 2 hours.
 
The CRF Field: "Number of attempts at weaning defined as continuous positive airway pressure (CPAP) trial (CPAP 5 cmH₂O plus PEEP 5 cmH₂O) of 2 hours duration" (in CRF Form: "Ventilation-Specific Information" in Daily assessments through extubation") counts the number of attempts at weaning as =1 each time that a CPAP 5 cmH₂O + PEEP 5 cmH₂O has been performed for 2 hours.
 
Number of patients achieving pressure support ventilation equal to 5 cmH₂O with PEEP equal to 5 cmH₂O for 2 hours (measure of weaning) by day 28
 
event = "Y" if at least one "Number of attempts at weaning defined as continuous positive airway pressure (CPAP) trial (CPAP 5 cmH₂O plus PEEP 5 cmH₂O) of 2 hours duration" >0 and date of daily collection (VSI DAT) is performed between Day 1 (date of 1st IMP intake) and Day 28.
 
otherwise event = "N" if all assessments are available (i.e., no missing values are present) between date of 1st IMP intake and Day 28 (or, in general, for all days of intubation) and they are all = 0
 
otherwise, event is missing.
 
Day 28= Day1 (date 1st IMP intake) + 27
 
Number of patients achieving pressure support ventilation equal to 5 cmH₂O with PEEP equal to 5 cmH₂O for 2 hours (measure of weaning) by hospital discharge
 
event = "Y" if at least one "Number of attempts at weaning defined as continuous positive airway pressure (CPAP) trial (CPAP 5 cmH₂O plus PEEP 5 cmH₂O) of 2 hours duration" >0 and date of daily collection (VSI DAT) is performed between Day 1 (date of 1st IMP intake) and date of discharge*.
 
event = "N" if all assessments are available (i.e., no missing values are present) between date of 1st IMP intake and Hospital discharge* and they are all = 0
 
otherwise, event is missing.
 
*date of discharge is collected in EOS; in the case it is missing it is taken from Visit date in "Hospital Discharge" .. If the subject has no hospital discharge it is assumed is because the subject was not discharged, so it is assumed that the event was during the hospitalization

Conversion of Time Intervals	
If a time interval was calculated in minutes, hours or days and needs to be converted into months or year the following conversion factors will be used:
 
 • 1 hour = 60 minutes • 1 day = 24 hours • 1 week = 7 days • 1 month = 30.4375 days • 1 year = 365.25 days

Standard/Forms/Template				
Title		Statistical Analysis Plan Template		
Code		Version	Effective Date	Page
PPD		01	29 Aug 2022	75 of 78

Parameter	Calculation
General rule	For calculation of a time interval, in case time is available, it is considered in the formula. Time intervals will be expressed in hours in if less than 24 hours and days if more than 24 hours.

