3.5.1 Primary endpoint

- Change in oxygenation index (OI) from baseline to day 7 [study day: date/time]
OI defined as: % mean airway pressure x FIO₂/PaO₂ (A difference between groups in 7-days OI of 6.6 points was significantly associated with 28-days mortality (Go et al., 2016). Thus, such a difference in the change in 7-days OI, ranked as the most important endpoint, will be valued as a proxy of clinical success)
- Ventilator free days (VFD) at day 28 [study day: date/time]

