4.4 Estimands

4.4.1 Primary estimands

The primary estimand #1 is defined by the following attributes:

- Population: Adult patients hospitalized for Acute Respiratory Distress Syndrome, as defined by the inclusion-exclusion criteria of the study.
- Variables: Oxygenation index (OI) at baseline and at day 7.
- Intercurrent events:
 - Death before Day 7, or at Day 7 if OI is not present, as a terminal event which precludes the observation of the variable, will be handled by the composite strategy. Day 7 value is derived using Study Day based on Date (i.e., Day 7= First IMP Intake + 6), since only date of death is collected. The event will be included in the estimand by imputing for OI at day 7, an extreme unfavorable value characterizing the treatment failure. The 90°

Standard/Forms/Template				
Title		Statistical Analysis Plan Template		
Code		Version	Effective Date	Page
PPD		01	29 Aug 2022	28 of 78

percentile of the distribution of the observed values will be used (the value will be rounded to present only one decimal place only for data presentation, not for imputation).

- For patients that at day 7 are extubated and OI is not evaluable, extubation will be handled by the composite strategy as an event which precludes the observation of the variable of interest. The event will be included in the estimand by imputing for OI at day 7 a sufficiently extreme favorable value characterizing the treatment success. The 10° percentile of the distribution of the observed values will be used (the value will be rounded to present only one decimal place, only for data presentation, not for imputation). A patient is extubated at day 7 if the patient results not intubated in the time range [First IMP Intake Date/Time +132h, First IMP Intake Date/Time +155h and 59 min].
- Treatment discontinuation, which may affect interpretation of the variable, will be handled by the treatment policy strategy. The occurrence of the intercurrent event will be irrelevant. All observed values will be used regardless of occurrence of the intercurrent event. Retrieved dropouts will be used for data imputation of all missing data (not due to death and not due to extubation), whichever is the reason of missingness.
- Population-level summary: Change in oxygenation index (OI) from baseline to day 7

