7.1.2 Sensitivity analyses

Standard/Forms/Template				
Title		Statistical Analysis Plan Template		
Code		Version	Effective Date	Page
PPD		01	29 Aug 2022	45 of 78

Sensitivity analyses are defined to assess the robustness of results on the two primary endpoints versus assumptions used in the statistical model for the main estimator.

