Primary endpoint "Change in oxygenation index (OI) from baseline to day 7 " [study day based on Date/time]	
OI derivation
 
OI is defined as: % mean airway pressure x FIO2/PaO2, derived as 100 x mean airway pressure x FIO2/PaO2. Following the estimand definition:
 
 - If patient dies before Day 7, or at Day 7 (Day 7 date = Day 1 date + 6, since only date of death -no time- is collected) and OI is missing: OI at day 7 = 90th percentile of the distribution of the primary variable at Day 7. - If patient at Day 7 is extubated* and OI is not evaluable (i.e., if the patient results not intubated* in the time range [First IMP Intake Date/Time +132h, First IMP Intake Date/Time +155h and59 min]): OI at day 7 = 10th percentile of the distribution of the primary variable at Day 7. - Otherwise, OI is set to missing. 
*intubation/extubation status at day 7: check intubations in "Extubation Summary" CRF form. Use the multiple entries of extubation/re-intubation: if the last record of intubations/extubation prior day 7 is an extubation and there are no intubations at day 7, it means the subject was extubated on Day 7. Subjects should reach day 7 to be eligible for this imputation.
 
Collection of data on FiO2/PaO2 and mean airway pressure
 
The implementation of the OI is based on 2 daily forms: "Mechanical Ventilation Parameters" for mean airway pressure, and "Lung Function" for the following parameters: PaO2/FIO2, FIO2, PaO2. FIO2/PaO2, used for the computation of OI, may be derived as 1/(PaO2/FIO2) or by using the individual values of PaO2 and FIO2 (when PaO2/FIO2 is missing) as described in the following section "Missing PaO2/FiO2 or mean airway pressure".
 
Missing PaO2/FiO2 or mean airway pressure
 
In case of missing PaO2/FiO2 for a specific visit, derive it based on the individual values of PaO2 and FiO2, if available. If PaO2 is not available set to missing (PaO2 won't be derived). The same applies for mean airway pressure, if not collected on a specific visit, the OI will be missing for that day.
 
Baseline derivation
 
1 - For each assessment performed on or prior treatment start date/time, derive OI as defined below.
 
1.1 Select the last record of mean airway pressure collected in that day (if on the same date of treatment start date, use only records with time <= time of first exposure to IMP)
 
1.2 - Select the "FiO2/PaO2" which is closest (and non missing) to the selected "mean airway pressure" and occurring on the same timeframe (but assessed on or prior treatment start date/time). Same timeframe here means that it should be considered the date/time of mean airway pressure (detected in step 1.1) +/- 12 hours BUT always considering prior to the first IMP intake. If there is any FiO2/PaO2 available in this timeframe, take that FiO2/PaO2 assessment. If there is no FiO2/PaO2 available in this timeframe, select the FiO2/PaO2 collected in the same exact date of the selected mean airway pressure (selected in step 1.1). If there is no such match, the OI baseline will set as missing.

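### Death by Day 7 is scored at the 90th percentile of measured oxygenation index (OI), so about one in ten measured patients scores worse than a dead patient, and no planned analysis tests that score

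*SAP*

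**What the plan says.** SAP 4.4.1 handles two events in the OI estimand by a composite strategy. Death ("Death before Day 7, or at Day 7 if OI is not present") is to receive "an extreme unfavorable value characterizing the treatment failure", and extubation a correspondingly favourable value. Table 3 in SAP 11.1.1 gives the numbers. For death: "OI at day 7 = 90th percentile of the distribution of the primary variable at Day 7". For extubation without an evaluable OI: "OI at day 7 = 10th percentile of the distribution of the primary variable at Day 7".

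SAP 4.4.1 takes the reference from measured data: the "percentile of the distribution of the observed values will be used". Table 3 requires both mean airway pressure and FiO2/PaO2 in the Day 7 window. For airway pressure it says "if not collected on a specific visit, the OI will be missing for that day". The reference group is therefore essentially patients still alive and ventilated. Neither section says whether the percentile is pooled or taken by arm.

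SAP 3.5.1 cites a 6.6-point difference in Day 7 OI and says that "such a difference in the change in 7-days OI, ranked as the most important endpoint, will be valued as a proxy of clinical success". SAP 7.1.2 defines sensitivity analyses as those that "assess the robustness of results on the two primary endpoints versus assumptions used in the statistical model for the main estimator".

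**The concern.** A 90th percentile is not an extreme value: one measured patient in ten is beyond it. The rule therefore falls short of the SAP's own description of the death score. It also differs from the other co-primary, where death scores 0 ventilator-free days, the floor of that scale.

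Two consequences follow. A patient heading for a very high Day 7 OI scores better by dying than by surviving. And a patient whose baseline OI is above the percentile and who dies contributes a negative change, which counts as improvement.

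At stake is how the endpoint that the SAP ranks first can be read. Part of its scale is set by the choice of 10th and 90th percentiles, and the plan contains nothing that would show how far the result depends on that choice.

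**Working it through.** **Inputs from the documents.** SD of OI 11.5; 60 evaluable patients, 1:1; about 66 enrolled; stated one-sided 95% width 5.35 points (SAP 3.3). Analysis: difference in mean change, adjusted for baseline OI (SAP 7.1.1.1). Reading: 6.6 points (SAP 3.5.1).

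**Assumed, because the documents do not give them.** Lognormal Day 7 OI with mean 12 to 18; 30% extubated and 12% dead by Day 7; baseline to Day 7 correlation 0.6; percentiles pooled over arms; 33 patients per arm.

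**1. The plan's own yardstick.** 0.465 × 11.5 = 5.35, as stated. The plain formula t(0.95, 58) × 11.5 × √(2/30) gives 0.432 × 11.5 = 4.96. Adding 80% assurance on the width, which is my assumption, gives about 0.464 × 11.5 = 5.33. The figure is used here only as a measure of scale.

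**2. How many patients score worse than dead.** 66 × 12% ≈ 8 dead and 66 × 30% ≈ 20 extubated, leaving about 38 measured. 38 × 10% ≈ 4 living patients above the death score. The 10% share follows from the definition; the count of 4 rests on the assumed rates.

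**3. One death.** In an arm of 30 it moves the arm mean by (P90 − would-be OI)/30. Take P90 = 28 (assumed):
- would-be OI 45: (28 − 45)/30 = −0.57, a better arm mean;
- would-be OI 20: (28 − 20)/30 = +0.27, a worse arm mean.

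The sign depends only on whether the would-be OI is above P90.

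**4. Recorded improvement.** Change = P90 − baseline, which is negative whenever baseline exceeds P90. In the simulations about 23% to 32% of deaths showed this, depending on the assumptions. Baseline adjustment offsets it only in part.

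**5. Two extra reparixin deaths** (simulation, assumed inputs above; negative favours reparixin):

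| The two who die are | Mean shift in OI difference |
|---|---|
| highest by would-be Day 7 OI | about −0.5 to −0.6 (towards reparixin in about 90% of trials) |
| sickest by baseline OI | about +0.15 |
| chosen at random | about +0.6 |

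**6. Dependence on assumptions (large-sample runs).**
- If the extra deaths are exactly the top 5% to 20% by would-be Day 7 OI, the false benefit is 0.4 to 1.6 points with 30% extubated and 0.5 to 2.2 with none.
- If they are the top 5% to 10% by baseline OI, the effect runs from +0.4 to +1.05 at correlation 0.3 to −0.3 to −1.0 at correlation 0.9.
- With 20% against 10% deaths, the extra deaths worsen reparixin until the correlation between death and would-be OI reaches about 0.85 to 0.95.

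**7. Would any planned analysis show it?**
- 7.1.2.1 changes only the missing-data model.
- 7.1.3.1 to 7.1.3.5 change the population, the imputation, the scale or the covariates and keep the death rule.
- 7.1.3.6 drops the dead and the extubated, so it conditions on survival.
- None varies the percentiles or places death last.

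**The case against.** The strongest reply is that excess deaths could not stay hidden. Ventilator-free days score death at 0, mortality at Day 28 and Day 60 is compared between arms, and the DMC watches for harm and may ask for unblinded efficacy data. The trial is descriptive and states no hypotheses, so 6.6 points is an aid to reading rather than a decision rule. Any composite sets its own scale, and using the observed minimum and maximum would lean on single outliers. Analysis 7.1.3.6 also gives a view without the imputed scores. All of this stands, and it limits the weight of the point. It does not supply a check on the scores, because 7.1.3.6 removes the deaths instead of ranking them.

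A reader might infer three stronger things that the documents do not support:
- **That extra deaths among the sickest patients generally improve the OI result.** This holds only where the would-be Day 7 OI exceeds the 90th percentile. With sickness judged at baseline, or deaths at random, the arm gets worse on average under the assumptions in step 5.
- **That the 27% to 45% mortality in protocol 2.6.2.3 measures the exposure.** That is disease-associated mortality by severity. No Day 7 figure is given.
- **That the rule could by itself produce a 6.6-point success.** Even the largest shift computed, 2.2 points, is a third of that.

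**Conclusion.** The point holds in a limited form. The death score does not match its stated purpose: about 10% of patients with a measured Day 7 OI score worse than a dead patient, and some deaths are recorded as improvement. These two facts, and the direction of the effect for patients above the percentile, follow from the SAP text.

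The size in points rests on the assumed OI distribution, event rates and correlation. In the unfavourable case with two extra deaths it is about 0.5 to 0.6 points. At 0.6 that is 0.6/5.35 ≈ 11% of the stated width and 0.6/6.6 ≈ 9% of the reading. This calls for an added sensitivity analysis; it does not undermine the trial.

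**What to change.** Add to SAP 7.1.2:
- A rank-based analysis of the OI co-primary, adjusted for baseline OI, with death worst, extubation best and measured OI ordered between. In simulation, two extra reparixin deaths then worsened the drug's result in 99% to 100% of trials.
- A repeat of the main analysis with more extreme percentiles, for example 5/95. About 5% of measured patients would still score worse than a dead patient, so this shows dependence on the choice and does not replace the rank analysis.

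State in SAP 3.5.1 that the 6.6-point reading is to be interpreted together with these results.

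Scoring death as the larger of the 90th percentile and the patient's own last OI should not be presented as a cure. A death with a last OI below the percentile would still score better than about one in ten measured patients.

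Cost: SAP wording and one or two extra tables from data already collected. The rank result is not in OI points, so it supports the main estimate and does not replace it. The additions count as pre-specified only if made before unblinding; otherwise the study report should label them post hoc.
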